When the *Dynesys Spinal System* and the *OPTIMA ZS Spinal System* are used on contiguous levels, they must be used with the *Zimmer DTO Implant*, rod-cord combination implant, and the *U & I Corporation OPTIMA ZS Transition Screw*. The indications for use for each level is as specified for each system.

Dynesys is comprised of a variety of pedicle screw sizes, tensioning cords and longitudinal spacers that are uniquely fitted for each individual case.

III. SUBJECT SELECTION

Patients participating in this study will be recruited from each investigator's standard patient population. All patients who meet the inclusion/exclusion criteria will be consecutively enrolled.

A. Inclusion Criteria

Patients must meet all of the following criteria to be enrolled into the study:

1. Patients must be skeletally mature between the ages of 20-80
2. Candidate for a posterior lateral fusion between T1-S1 with autograft
3. Degenerative spondylolisthesis with evidence of neurologic impairment, or failed previous fusion (pseudarthrosis)
4. Symptoms of leg and/or back pain
5. Non-responsive to conservative/non-surgical treatment for at least three (3) months
6. Must be willing and able to comply with study requirements; including complete necessary study paperwork and return for required follow-up visits.

B. Exclusion Criteria

Patients who meet any of the following criteria should not be enrolled into the study:

1. Active systemic or local infection
2. Obesity
3. Use of interbody device
4. Pregnancy
5. Mental illness
6. Incarceration
7. Alcohol or drug abuse
8. Severe osteoporosis or osteopenia
9. Use in the cervical spine
10. Sensitivities/allergy to metals, polymers, polyethylene, polycarbonate urethane and polyethylene terephthalate
11. Soft tissue deficit not allowing sound closure
12. Any medical or physical condition that would preclude the potential benefit of spinal implant surgery
13. Congenital abnormalities, tumors or other conditions that would prevent secure component fixation that has the potential to decrease the useful life of the device
14. Active malignancy or other significant medical comorbidities
15. Any medical or mental condition which would put the patient at high risk due to the severity of surgery
16. Inadequate pedicles of the thoracic, lumbar and sacral vertebrae
17. Patient unwilling or unable to follow postoperative instructions

IV. STUDY PROCEDURES AND DATA COLLECTION

Table 1: Study Schematics

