A meta-analysis was done using the same methodology as was used for the primary endpoint, fusion rate. When sufficient data were available for baseline characteristics, point estimates and 95% confidence intervals were generated for use to assess comparability of baseline data in the historical literature to the experimental data. The data were extracted from the same literature that was used to obtain an estimate for the primary endpoint of fusion rate. The first table below represents the detail available for use in comparison of the treatment group to the literature control data for the baseline characteristics and the second table contains the point estimates of interest for the baseline characteristics from the literature. Comparability will be inferred if the rates of males or smoking status in the experimental group are contained in the respective 95% confidence intervals established using the literature control rates. Comparability for age will be inferred if the point estimate for mean age in the experimental group is contained in the range presented for the historical control. Additionally, a frequency distribution of pre-operative diagnoses, from both the experimental group and what is available in the literature control group will be done to ensure comparability between the data from each.

Point Estimates Demographic Endpoints					
Age	Mean	STD	MIN	MAX	
Weighted Average	55.9706	NA	40.72783	75.31652	
Random Effects	Rate	SE	LCL	UCL	
Gender (Male)	35.78%	3.14%	28.78%	42.77%	
Smoking Status	39.11%	7.13%	21.64%	56.57%	
BMI - not enough information					

Demographic Endpoints	N	Age	Gender (% Male)	Smoking Status (%)	BMI
Acharya 2008	22	55	36.4%		
Chen 2005*	74	61.6	20.3%		
Cheng 2009	66	48	52.9%	0.221	
Christensen 2002	63	46	41.3%	0.65	
Christensen 2002	71	45.5	37.0%		
Dimar 2006	45	52.7	44.4%	0.222	
Fernandez-Fairen_1 2007	41	61.42	35.7%		
Glassman 2008	52	69.9	32.7%	0.173	28.1 +/-6.1
Lee 2009	182	59	33.5%		
Moller 2000	37	39	43.2%	0.57	
Thalgott_1 1997	21	55		0.429	
Thalgott_2 1997	21	45		0.523	
Wang 1998	94	67.03	17.0%		

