To assure that baseline characteristics of the history control data are similar to those found in the experimental data, the demographic characteristics from the study data will be reviewed to confirm that the characteristics of age, gender, smoking status, and preoperative diagnosis in the test data are similar to the data that existed for the historical control data. The rate of males and rate of smokers will be checked against the 95% confidence interval found in the point estimate table. The distribution of preoperative diagnoses will be tested for no difference between the historical control and the test group. The average age will be checked to assure that it is in the range from 41 to 75. If any differences are noted, patients with extreme data will be removed until the rates and means of the test population do reside within the bounds determined by the meta-analysis. If needed, more patients will be enrolled in the test group to assure that the sample size is sufficient for inferential testing.

B. Primary Analysis: Fusion Status

Fusion success will be defined as evidence of bridging bone and angulation of <5° and translation of <3mm at treated levels at 24 months. Radiographic assessment will determine for each patient a fusion status, either fused or not fused. The primary endpoint is fusion status at Month 24. Efficacy will be confirmed by the achievement of fusion in the experimental group when compared to the rate established in a literature control. Normand (1999) provided the direction for the meta-analysis¹. The details of that analysis included creating population mean and variance estimates using a weight of the inverse of the variance. (See pp. 335-336 for complete description of the algorithm) A point estimate of 80.6% with a standard error of 2.6% was established. The 95% confidence interval for this point estimate is (75.0%, 86.3%).

If Month 24 fusion status cannot be determined, but fusion was determined to have occurred earlier, the Month 24 status will be considered fused. Otherwise, subjects without earlier fusion who are missing Month 24 values will be excluded from primary analysis.

For the purpose of a sensitivity analyses, all subjects excluded as described above for a missing Month 24 fusion status will be defined as not fused.

C. Primary Analysis: Safety Endpoints and Evaluation

Subjects will be clinically evaluated for adverse experiences and functional outcomes over the course of 24 months.

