Removal and Refusion				

E. Baseline and Operative Analysis

Baseline summaries will be chosen to be appropriate for the scale and distribution of the measures being analyzed. Statistical methods will be the same as described above for the non primary endpoint analyses.

F. Missing data

Except for the primary analysis, if a value, at any assessment is not available for analysis, it will be excluded from summaries.

G. Study Hypothesis and Sample Size Determination using a Literature Control

Study Hypothesis

The hypothesis is Dynesys fusion rate is non-inferior to the historical literature sample data estimated fusion rate of 80.6%. This hypothesis will be assessed by testing that the difference between the experimental rate (p_e) and the historical control rate (p_c) is not worse than 10%. The non-inferiority test will be inferred if the lower limit of the 95% confidence interval around the **treatment difference** between 2 groups is greater than $\delta = -10\%$.

$$H_0: p_e - p_c \leq -0.10$$

$$H_1: p_e - p_c > -0.10$$

Sample Size

Sample size for the Dynesys Post-Market Surveillance Study was estimated using SAS, Proc Power with a testing level alpha (Type I) error level of 0.05, 80 percent statistical power, a meaningful difference of 10%, and a success rate for lumbar fusion from the literature historical

control group of 80.6% (0.806). For this set of criteria, the sample size was 134, without adjustment for attrition. With a 20% attrition sample added, this would result in a sample size of 168.

Sample size estimates are presented in Table 2.

Table 2: Proposed Sample Sizes

Primary Endpoint	Difference	Predicted Success	Type I Error	Power	N Patients
Radiographic Success (Fusion)	10%	80.6%	0.05	80%	168

VI. TIMELINE

A. Clinical Trial Agreement

No portion of this protocol will be implemented until both copies of the Clinical Trial Agreement have been completed by both parties.

Table 3: Study Timeline

Study Timeline	Sponsor Expectation
Expected date of Study Initiation	March 2012
Expected date of first IRB Approval(s)	January 2012
Expected monthly number of sites obtaining IRB approval	1
Expected subject enrollment initiation	March 2012
Expected average number of subjects to be enrolled/month	7
Expected Date of Subject Enrollment Completion	March 2014
Expected date of Subject follow-up Completion	March 2016
Reports	
Interim Postmarket Surveillance Study Report	Every 6 months through 2 years, annually thereafter

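### Section V.A supports similarity of diagnosis mix with the literature control by a test of no difference that has no margin, interval or power, so a non-significant result cannot show similarity

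*Combined protocol and SAP*

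**What the plan says.** Section V.A gives the purpose of the baseline checks as "To assure that baseline characteristics of the history control data are similar to those found in the experimental data". Four characteristics are named: age, gender, smoking status and preoperative diagnosis.

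- Gender and smoking are judged by whether the trial rate lies inside a literature 95% confidence interval. Mean age is judged by whether it lies in a literature range.
- For diagnosis the rule is: "The distribution of preoperative diagnoses will be tested for no difference between the historical control and the test group". No bound is given.
- An earlier paragraph of V.A describes the diagnosis check differently. It promises "a frequency distribution of pre-operative diagnoses, from both the experimental group and what is available in the literature control group will be done to ensure" that the two sources are comparable, with no rule for reading the table.
- The consequence of a mismatch is: "If any differences are noted, patients with extreme data will be removed until the rates and means of the test population do reside" inside the meta-analysis bounds. Those bounds do not cover diagnosis.

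Section III.A, item 3, admits two diagnoses: degenerative spondylolisthesis with neurologic impairment, and pseudarthrosis after an earlier fusion. The primary test (V.B and V.G) compares the single-arm fusion rate with a literature rate of 80.6% and a 10-point margin. V.B, V.D and V.G do not adjust or stratify fusion by diagnosis. The poolability checks in V.A do look at primary diagnosis, but they compare trial subgroups with each other, not the trial with the literature.

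**The concern.** A test of no difference takes no difference as its null hypothesis. Failing to reject it is weak evidence of similarity unless the test had high power against differences that matter. An equivalence test would need a margin, and none is given, so the sentence can hardly mean one.

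With an external control, comparable case mix is what supports the fusion comparison. If diagnosis affects fusion and the trial holds more of the easier diagnosis than the articles do, the trial's fusion rate rises through mix alone and uses up part of the 10-point margin. A shift the other way penalises the device. The plan as written could accept either.

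**Working it through.** **Inputs from the documents.** V.G: "the sample size was 134, without adjustment for attrition", and 168 with 20% attrition; literature fusion rate 80.6%; margin 10 points. V.A demographic table: the 13 rows sum to 789 patients, which is the most that could contribute diagnosis data from those rows.

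**The plan's own figure.** The one-sample formula with two-sided 0.05 and 80% power gives n = [1.960 × √(0.806 × 0.194) + 0.842 × √(0.706 × 0.294)]² / 0.10² = 134.2, against the stated 134. Attrition: 134 / 0.80 = 167.5, so 168. This calculation concerns fusion only; no power is stated for the diagnosis test.

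**Assumptions, because the documents are silent.** Two-sided 5% pooled two-proportion test, two diagnosis groups, 100 to 789 literature patients with diagnosis data, literature share 5% to 50%, and a true trial share 10 points higher.

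**Miss rate.** With trial share p_T (n_T patients), literature share p_L (n_L patients) and pooled share p̄:

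- s0 = √[p̄(1 − p̄)(1/n_T + 1/n_L)]
- s1 = √[p_T(1 − p_T)/n_T + p_L(1 − p_L)/n_L]
- miss rate ≈ Φ[(1.96 s0 − 0.10)/s1]; the opposite tail is negligible.

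Example, 50% to 60%, 134 against 789: p̄ = (134 × 0.60 + 789 × 0.50)/923 = 0.5145; s0 = 0.0467; s1 = 0.0459; (0.0915 − 0.10)/0.0459 = −0.185; Φ = 0.43.

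Results at 134 trial patients:

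| Share, literature to trial | n_L = 100 | 200 | 400 | 789 |
|---|---|---|---|---|
| 50% to 60% | 67% | 57% | 48% | 43% |
| 20% to 30% | 59% | 45% | 34% | 28% |
| 10% to 20% | 45% | 28% | 17% | 12% |
| 5% to 15% | 30% | 14% | 7% | 4% |

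Simulation of the same test agrees within about 1 point in the first two rows; separate runs put the 43% cell at 42% to 43% and the 59% cell at 59% to 60%. In the last two rows the approximation runs up to 3 points high: simulation gives 44% and 27% at n_L = 100, and 12% and 3% at n_L = 789. With all 168 patients and n_L = 789, the miss rate is 34% (50% share) and 21% (20% share).

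In the worked example the test does not reject until the observed difference exceeds about 1.96 × 0.0467 = 9.2 points. A 9-point observed imbalance would pass.

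**What a missed shift could do to the fusion test.** Assume the two diagnoses differ by 10 to 30 points in fusion rate; the documents give no figure. A 10-point shift in mix then moves the trial rate by 0.10 × 10 = 1 point to 0.10 × 30 = 3 points. With n = 134 and the control fixed at 80.6%, non-inferiority needs a lower 95% limit above 70.6%, which means at least 105 of 134 fused (Wald and Wilson agree). For a device truly 10 points worse, the exact binomial probability of passing is:

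| Mix adds | 0 points | 1 | 2 | 3 |
|---|---|---|---|---|
| Control fixed | 2.8% | 4.8% | 7.9% | 12.4% |
| Literature SE of 2.6% included | 3.0% | 4.8% | 7.3% | 10.8% |

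**The case against.** Several points on the other side stand.

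- The plan never says outright that non-significance establishes comparability. Its explicit inference rule covers sex, smoking and age only; for diagnosis there is a frequency table and one sentence on testing. The reading here is the natural one, not the only one.
- A reader might infer that the plan has a definite miss rate, such as two thirds. It does not. The result depends on alpha, the diagnosis shares and the number of literature patients with diagnosis data, none of which is stated. For uncommon diagnoses and the full 789 the test would catch most 10-point shifts.
- A reader might also infer that this one test certifies the control as a whole, or that diagnosis share sets the fusion rate. Diagnosis is one of four checks, and no fusion rate by diagnosis is given, so one can say only that diagnosis may affect fusion.
- The bounds used elsewhere are not necessarily stricter. The smoking interval runs from 21.64% to 56.57%. With 134 patients, a true 10-point shift from 39.11% stays inside it about 95% (up) or 98% (down) of the time. Low sensitivity is a feature of V.A in general.
- The false-pass figures assume a favourable shift that has already occurred and been missed. At the low end the rise is only from 2.8% to 4.8%.

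Detecting a difference is not safe either: it triggers the removal rule, which has no stopping point for diagnosis. None of this makes a non-significant result evidence of similarity.

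**Conclusion.** The point holds in a limited form. The diagnosis check is meant to confirm similarity, but its only decision tool is a test that cannot do so, with no stated error rate. For mid-range shares the illustrated miss rate for a 10-point shift is high (28% to 67% at shares of 20% to 50%); for shares of 5% to 10% with all 789 literature patients it is low (3% to 12%). If a missed shift added 1 to 3 points to fusion, the chance of wrongly passing a device 10 points worse would rise from about 3% to between 5% and 12%. Both sets of figures rest on the assumptions listed above. They show that the criterion is unreliable, not that the trial's case mix will differ. The wording should be changed before analysis; the primary test itself need not be.

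**What to change.** In V.A, replace the sentence on testing diagnoses with the following:

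1. Report each diagnosis share in the trial and in the articles that report it, with the difference and its 95% CI. Do not infer comparability from a non-significant p-value.
2. Report Month 24 fusion with a 95% CI separately for degenerative spondylolisthesis and pseudarthrosis. The Patient History form lets more than one primary indication be ticked, so prespecify how patients with both are assigned.
3. Where the articles report diagnoses that the trial also enrols, add a sensitivity analysis of the primary test. It uses the reweighted rate Σ w_k p_k, where w_k is the literature share of diagnosis k among the shared diagnoses and p_k the trial's fusion rate in it. Its sampling variance is Σ w_k² p_k(1 − p_k)/n_k, where n_k is the number of trial patients with diagnosis k. If there is no usable overlap, state that the analysis is not feasible.
4. State that no patient will be removed from the analysis because of the diagnosis comparison, since no bound exists for it.

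An equivalence margin is not proposed because it would often be underpowered. With an assumed margin of ±10 points, two one-sided 5% tests, a 50% share and 134 against 789 patients, power at zero true shift is 2Φ(0.10/0.0467 − 1.645) − 1, or about 38%.

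Cost: SAP wording, two tables and one conditional analysis. Primary indication is already collected, and literature diagnoses are already to be tabulated where available. Estimates will be imprecise if one diagnosis group is small, and the reweighting covers only articles that report diagnosis.

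### Confidence intervals for a pooled literature average are used as pass/fail limits for one new study, with patients removed until the trial fits; the age bounds are undefined

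*Combined protocol and SAP*

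**What the plan says.** Section V.A (Analysis Population) sets up a baseline comparison with the literature control.

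- **Sex and smoking:** "Comparability will be inferred if the rates of males or smoking status in the experimental group are contained in the respective 95% confidence intervals" built from the literature. The point-estimate table gives rate, SE and limits under a random-effects label: males "35.78% 3.14% 28.78% 42.77" and smokers "39.11% 7.13% 21.64% 56.57" (all percentages).
- **Age:** "Comparability for age will be inferred if the point estimate for mean age in the experimental group is contained in the range presented for the" (literature control). The age row, labelled as a weighted average, gives mean, SD, minimum and maximum as "55.9706 NA 40.72783 75.31652". The following paragraph applies this as: "The average age will be checked to assure that it is in the range from 41 to 75".
- **Consequence:** the same paragraph says that if differences are seen, patients with extreme data are taken out until the trial's rates and means lie within the bounds. Further patients may be enrolled if the sample becomes too small.

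The study table in the same section lists 13 rows with mean ages, 11 with a male rate and 7 with a smoking rate. The lowest mean age is in the row "37 39 43.2% 0.57" (N, age, male, smoking) and the highest in the row "52 69.9 32.7% 0.173".

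**The concern.** A confidence interval for a pooled mean says how well the average of the literature is known. It narrows as studies are added, however much the studies differ from each other. Used as an acceptance limit for one further study, it will often reject a study as typical as those that went into it.

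That would matter little if the check were only reported. Here a failure changes who is analysed. Section V.A begins by defining the analysis population as all consented subjects meeting the entry criteria, and then allows some of them to be removed on baseline characteristics. For a yes/no characteristic such as sex, no individual is extreme, so the rule does not say which patients leave, and it does not say when the check is made. Smoking is also prognostic in the plan's own material: the Dynesys Instructions for Use (3.1 Precautions) state that smokers have more non-union. Removing smokers to meet a limit could therefore raise the observed fusion rate, which is the primary endpoint.

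For age, the reader cannot tell what the bounds measure, so cannot judge whether they suit a group mean.

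**Working it through.** **1. Reproduce the sex and smoking limits.** Formula: mean ± t(k−1) × SE, with k the number of rows.
- Males, k = 11, t = 2.228: 35.78 ± 2.228 × 3.14 = 28.78 to 42.78 (stated 28.78 to 42.77).
- Smokers, k = 7, t = 2.447: 39.11 ± 2.447 × 7.13 = 21.66 to 56.56 (stated 21.64 to 56.57).

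The limits are correct 95% intervals for the pooled mean.

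**2. Does the SE include between-study variance?** The fixed-effect SE, 1/√Σ[n/(p(1−p))], from the tabulated rates and Ns is 1.66% for males and 2.50% for smokers. The stated 3.14% and 7.13% are larger, so it does.

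**3. Source rows against the limits.**
- Males outside: 17.0, 20.3, 43.2, 44.4, 52.9%, which is 5 of 11.
- Smokers outside: 17.3, 57, 65%, which is 3 of 7.

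**4. Between-study SD (τ).** Heterogeneity is large: Q = 41.1 on 10 df for males and 57.3 on 6 df for smokers. Two estimates of τ:
- DerSimonian-Laird: 0.100 (males), 0.197 (smokers).
- The τ that gives the plan's own SE from the tabulated rates: 0.083 and 0.173.

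**5. Chance that a new study from the same literature passes.** The new rate is taken as normal around the plan's pooled mean μ, with s = √[τ² + μ(1−μ)/n]. The pass probability is Φ((U−μ)/s) − Φ((L−μ)/s). The extremes are:

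| Check | τ | n | s | Half-width / s | Pass |
|---|---|---|---|---|---|
| Sex | 0.100 | 134 | 0.108 | 0.65 | 48% |
| Sex | 0.083 | 168 | 0.091 | 0.77 | 56% |
| Smoking | 0.197 | 134 | 0.202 | 0.87 | 61% |
| Smoking | 0.173 | 168 | 0.177 | 0.99 | 68% |

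Simulating whole-patient counts gives nearly the same result: 48–55% for sex and 61–68% for smoking.

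**6. What failing would cost.** Take one source row's male rate, 20.3%.
- Of 168 enrolled: 0.203 × 168 ≈ 34 men. To reach 28.78%, at most 34/0.2878 = 118 patients can remain, so about 50 women are removed. Section V.G requires 134 before attrition is added.
- Of 134 evaluable: 0.203 × 134 ≈ 27 men, and 27/0.2878 = 93.8, so at most 93 remain.

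At another row's 65% smoking rate, 168 patients include about 109 smokers. Requiring (109 − x)/(168 − x) ≤ 0.5657 gives x ≥ 32.1, so 33 smokers are removed.

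**7. Prediction interval for one new study of 134 patients.** Formula: μ ± t(k−2) × √[τ² + SE² + μ(1−μ)/n].
- Males, t = 2.262: about 10% to 61% with τ = 0.100; about 14% to 58% with τ = 0.083.
- Smokers, t = 2.571: from below 0 (truncated to 0%) to about 94% with τ = 0.197, or 88% with τ = 0.173.

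**8. Age.** The N-weighted mean of the 13 rows is 44171.24/789 = 55.98 (stated 55.97), so the table appears to be the source of the mean. The tabulated means run from 39.0 to 69.9, and the weighted mean ± 1.96 × the unweighted between-study SD of 9.32 is 37.7 to 74.2. Neither gives 40.73 to 75.32. The 41–75 in the text is a faithful rounding of that row.

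**The case against.** The best defence of the sex and smoking limits is that they are deliberately strict. The primary test compares the trial with one pooled fusion rate, 80.6%, so it is coherent to ask that the trial resemble the pooled population and not merely some study in a varied literature. If the trial's underlying male rate equalled the pooled mean exactly, sampling error alone would let it pass about 91–94% of the time, and almost always for smoking. This stands as a reason to show the comparison. It does not justify removing patients, since most of the chance of failing comes from ordinary differences between studies.

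Three stronger readings are tempting, and the documents do not support them.

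- A reader might infer that the intervals are miscalculated or ignore between-study variation. They are correct for a pooled mean, and their SEs include that variation.
- A reader might infer that the age bounds are an arithmetic error, because they differ from 39.0 and 69.9. The row is labelled a weighted average and carries five decimals, so its minimum and maximum may be averages of each study's youngest and oldest patients. That is an assumption; the inputs are not in the documents. The age bounds are unexplained, not shown to be wrong.
- A reader might object that the age bounds are not centred on 55.97. A range need not be; 39.0 to 69.9 has its midpoint at 54.45.

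The age discrepancy is also remote in practice. It changes the outcome only for a trial mean of about 39.0–40.7 or 69.9–75.3.

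**Conclusion.** The concern holds for how the limits are used. Correctly calculated intervals for a pooled mean serve as acceptance limits for a single study, and failing them leads to exclusion from the primary analysis. A trial that is an ordinary member of this literature has roughly an even chance of failing the sex check and about a one-in-three chance or somewhat more of failing the smoking check. These chances assume that the trial is exchangeable with the source rows, that study rates are approximately normal, and that τ lies between the two estimates used. The counts of source rows outside the limits need none of these assumptions.

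The removal figures are illustrations at rates seen in the literature, not forecasts. The documents do not show that exclusions would be chosen by outcome; the point is that the rule leaves the choice open, and that for smoking the likely direction of bias favours the device.

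For age, the supportable statement is that the bounds are undefined and not reproducible from the table. If they average individual extremes, they form a range for patients and are not a suitable limit for a group mean.

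**What to change.** In Section V.A:

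1. Delete the rule that removes patients until the bounds are met, and keep all eligible patients in the primary analysis.
2. Report age, sex and smoking beside the literature values. Treat a value outside the bounds as a stated limit on comparability.
3. Define the age minimum and maximum, or replace them with the range of tabulated study means, 39.0 to 69.9.
4. If intervals are shown for sex and smoking, label the present ones as confidence intervals of the pooled mean and give the prediction intervals from step 7 beside them, as description only. They should not become new pass/fail limits: the smoking interval would let almost any trial through.

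The work is a text change and a few intervals from data already held. The price is that the comparability check becomes descriptive and shows openly how little it can establish. In return, the primary analysis no longer depends on post-hoc exclusions, and extra enrolment to replace removed patients is no longer needed.
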